### **6.1.2 Double-blind Treatment Period (Day 1 to Week 26)**

Eligible patients will be randomized on Day 1 (Visit 3). In order to qualify for randomization, patients must also demonstrate compliance during the single-blind placebo Run-in phase based upon tablet count ( $\geq 80\%$ ) and, as assessed, at the Investigator's discretion.

Randomization will be stratified by:

- HbA1c at Screening ( $\leq 8.5\%$  and  $> 8.5\%$ )
- SBP at Screening ( $< 130$  mmHg and  $\geq 130$  mmHg)
- CKD stage (3A, 3B) based on Screening eGFR (15)(16)(17).

Following randomization, patients will be treated in a double-blind manner for 52 weeks. A total of approximately 780 patients  $\geq 18$  years of age (or  $\geq$  legal age of the majority, whichever is greater) are planned to be randomly assigned 1:1:1 to the following 3 treatment groups:

- Placebo, given as two (2) placebo tablets (identical to sotagliflozin 200 mg in appearance), once daily, before the first meal of the day
- Sotagliflozin 200 mg, given as 2 tablets: 1 sotagliflozin 200 mg tablet and 1 placebo tablet (identical to sotagliflozin 200 mg in appearance), once daily
- Sotagliflozin 400 mg, given as two (2) 200 mg tablets, once daily, before the first meal of the day.

Fasting glucose (plasma or serum) and HbA1c results will be masked to study sites and patients after randomization and until study end. To prevent partial unblinding, UGE and UGCR results will be masked to study sites and patients, and the central laboratory urine dipstick analysis will not include the measurement of urine glucose.

Quantitative urine glucose, albumin, calcium, phosphorus, magnesium, and creatinine will be measured separately at all on-site visits (except for Visits 6, 8, 10, and 12) by the central laboratory.

All visits will be on-site visits.

If a patient discontinues treatment with investigational medicinal product (IMP) early during the Treatment Period, the patient will have Premature End of Treatment (EOT) Visit, and a Follow-up Visit, 4 weeks ( $\pm 5$  days) after the last dose of IMP. In addition, every effort will be made to have all patients return to the site at the time corresponding to their scheduled visits, particularly the Weeks 26 and 52 Visits.

If a patient does not agree to site visits, he/she will be contacted by telephone to inquire their safety information, particularly at the time of the initially scheduled end of study (EOS).

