#### 9.1.3 Other efficacy endpoints

To compare sotagliflozin 400 mg and 200 mg versus placebo, respectively, in terms of:

- Change from Baseline in SBP at Weeks 26 and 52 for patients with Baseline SBP  $\geq$ 130 mmHg
- Change from Baseline in SBP at Weeks 26 and 52 for all patients
- Change from Baseline in HbA1c at Week 52
- Change from Baseline in FPG at Week 52
- Change from Baseline in body weight at Week 52
- Change from Baseline in eGFR.
- Proportion of patients requiring rescue for hyperglycemia during 26-week double-blind Treatment Period.
- Change from Baseline in:
  - Cystatin C

- UGE
  - UGCR
  - Fructosamine
  - NT-proBNP.
- Proportion of patients with progression to end-stage renal disease (ESRD) (dialysis or transplant) at Week 4 or any time later during the trial.
  - Proportion of patients with >50% decline in eGFR from Baseline to Week 26 and Week 52.
  - Proportion of patients with progression from normal to microalbuminuria or from microalbuminuria to macroalbuminuria from Baseline at Week 26 and Week 52.
  - Proportion of patients with improvement from microalbuminuria to normal to or from macroalbuminuria to microalbuminuria from Baseline at Week 26 and Week 52.
  - Change from Baseline in SBP at Week 12 for patients with Baseline SBP <130 mmHg.
  - Change from Baseline in DBP at Week 12 for all patients and the subset of patients with Baseline DBP  $\geq$ 80 mmHg.

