#### **9.1.4.7 Use of rescue medication for hyperglycemia**

The use of rescue medications for hyperglycemia will be assessed and reported throughout the double-blind Treatment Period. Routine alerts on FPG will be sent to the Investigator from the central laboratory to ensure that glycemic parameter results remain within predefined thresholds. For details and further actions should FPG values fall above thresholds, refer to [Section 8.2.1](#).

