#### **10.3.4 Handling of patients after permanent treatment discontinuation**

Every effort should be made to maintain patients in the study. Patients should be followed up according to the study procedures as specified in this protocol up to the scheduled date of study completion, or up to recovery or stabilization of any AE to be followed up as specified in this protocol, whichever comes later.

If a patient decides to discontinue study treatment early, a Premature EOT Visit (see [Section 10.1.3.2](#)) should be scheduled prior to treatment discontinuation, if possible. If not possible, the Premature EOT should be scheduled as soon as possible after treatment discontinuation. In the case of early discontinuation, no sample for measuring plasma concentration should be taken at the Premature EOT Visit, or at any subsequent visits. For patients who discontinue treatment but remain in the study, the remaining study visits should occur as scheduled where possible. The IRT should be notified of EOT.

All cases of permanent treatment discontinuation should be recorded by the Investigator in the appropriate pages of the e-CRF.

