### 11.2 DISPOSITION OF PATIENTS

The total number of patients for each of the following categories will be presented in the CSR.

- Screened patients: patients who have signed the ICF.
- Run-in patients.
- Randomized patients: patients with a treatment kit number allocated and recorded in IRT database, regardless of whether the treatment kit was used or not.
- The safety population (ie, randomized and treated patients).
- The ITT population, as defined in [Section 11.3.1.1](#).

- The randomization strata (HbA1c at Screening [ $\leq 8.5\%$ ,  $> 8.5\%$ ], Screening SBP [ $< 130$  mmHg,  $\geq 130$  mmHg], and CKD stage [3A, 3B]). The discrepancy between the strata assigned by IRT and the information reported on e-CRF will be listed for all randomized patients.
- Patients who have completed the 26-week double-blind Treatment Period.
- Patients who discontinued the IMP during the 26-week double-blind Treatment Period, and the reasons for treatment discontinuation.
- Patients who have completed the 52-week entire Treatment Period.
- Patients who discontinued the IMP during the 52-week entire Treatment Period, and the reasons for treatment discontinuation.
- Patients who have completed the study.
- Patients who discontinued the study, and the reasons for study discontinuation.

For all categories of patients except screened, percentages will be calculated using the number of randomized patients as denominator for each treatment group.

A list of patients prematurely discontinued from the treatment, along with reasons for discontinuation, will be provided. Similarly, a list of patients prematurely discontinued from the study, along with reasons for discontinuation, will be provided.

Patients treated but not randomized, patients randomized but not treated and patients randomized but not treated as randomized will be identified and described in separate listings. The safety experience of patients treated and not randomized will be reported separately, and these patients will not be in the safety population.

For any patient randomized more than once, only the data associated with the first randomization will be used in any analysis population. The safety experience associated with any later randomization will be assessed separately.

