2.4.4.3 Analyses of other efficacy endpoints

The analysis of other endpoints (see [Section 2.1.3](#)) will be descriptive with no formal testing. Summary statistics at scheduled visits based on observed value will be provided by each treatment group. Summary statistics of eGFR at scheduled visits will be presented for overall population and each CKD stratum. Graphical presentations will also be used to illustrate trends over time as appropriate.

The number (%) of patients who used rescue therapy will be provided by treatment group during the 26-week core (see [Section 2.5.4](#)) and the 52-week entire double-blind treatment periods. A KM curve for the time to first rescue therapy will be presented during the 26-week core treatment

period and 52-week entire double-blind treatment period respectively (see [Section 2.5.4](#)). The list of patients who used rescue therapy will also be provided.

ESRD is defined as: 1) dialysis that persists for a duration of ≥ 90 days, or positively adjudicated as ESRD if dialysis < 90 days; 2) eGFR < 15 ml/min/1.73 m² sustained for at least 30 days or positively adjudicated as chronic; or (3) renal transplant. The number (%) of patients with progression to ESRD at Week 4 or any time later during the study will be summarized. The same analysis will be provided during the period from the date of the first administration of double-blind IMP (or the date of randomization if not exposed) to Week 4 (exclusive). A KM plot will be provided for time to first occurrence of ESRD up to Week 26 and the end of study respectively (see [Section 2.5.4](#)).

The number (%) of patients with $> 50\%$ decline in eGFR from baseline at each scheduled visit (including Week 26 and Week 52) will be presented. The same analysis will be presented from Week 4 at each scheduled visit afterwards (including Week 26 and Week 52). A KM plot will be provided for time to first occurrence of $> 50\%$ decline from baseline in eGFR up to Week 26 and the end of the study respectively (see [Section 2.5.4](#)).

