As specified in the study protocol, laboratory data from scheduled visits are reported by central laboratories. The local results will not be used in the efficacy analyses or in the definition of baseline for both safety and efficacy analyses. In the safety analyses, for parameters with PCSA defined based on normal range, local results will only be used in the PCSA summary if they are accompanied by a local laboratory normal range. For parameters with PCSA not defined based on normal range, local results will be used in PCSA summary as appropriately.

When a patient has more than 1 measurement from the central laboratory for the same laboratory parameter on the same date, the average of the measurements will be used. For the same laboratory parameter, if a patient has more than 1 measurement on different dates for the same scheduled visit, the value closest to the date of the visit will be used for the scheduled visit. When the values for the same scheduled visit are equidistant, the last value should be used for the scheduled visit. Similar rules will be applicable to a patient who has more than 1 set of measurements for the same vital sign parameter (ie, SBP, DBP, or HR) on the same date.

26-week double blind core treatment period

The 26-week double-blind core treatment period is the time from first administration of double-blind IMP to the last administration of double-blind IMP on or before Visit 9/Week 26 (or Day 182 if Visit 9/Week 26 date is missing). This is for defining EOT status at Week 26 and analyzing selected efficacy parameters (eg, rescued patients) during 26-week core treatment period.

TEAE period for the 26-week double blind core treatment period

The TEAE period for the 26-week double-blind core treatment period is 1) the time from the first administration of the double-blind IMP up to 10 days (1 day for hypoglycemia) after the last administration of IMP if the patient discontinued treatment on or before Visit 9 (or Day 182 if Visit 9 date is missing), or 2) the time from the first administration of the double-blind IMP to the administration at Visit 9/Week 26 (or Day 182 if Visit 9/Week 26 date is missing) if the patient remained treated beyond Visit 9/Week 26. This is for the purpose of safety analyses during the 26-week core treatment period.

26-week core study period

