The 26-week core study period is the time from first administration of double-blind IMP to Visit 9/Week 26 (or Day 182 if Visit 9/Week 26 date is missing) or the end of TEAE period for the 26-week double-blind core treatment period (as defined above) whichever is later. This is for defining EOS status at Week 26.

Time to event analysis

For time to event analysis/KM plot, time to event (eg, treatment discontinuation, rescue therapy, hypoglycemia, ESRD, etc) is defined as the number of days from the date of the first administration of double-blind IMP (or the date of randomization if not exposed) to the start date of the first occurrence of the event during the respective analysis period.

Statistical Analysis Plan

Version: Final 3.0

Lexicon Pharmaceuticals Protocol No. EFC14837

Date of Issue: 21 November 2019

Covance Study ID:000000155205

Patients who did not experience any event during the respective analysis period are considered censored observations. The censoring rules are defined below.

Table 5 - Censoring date of time to event for 1st and 2nd step analysis

Time to event	Censoring date at Week 26 (1 st step analysis)	Censoring date at EOT/EOS (2 nd step analysis)
Treatment discontinuation due to any reason	Not applicable	EOT
Treatment discontinuation due to AE	Not applicable	EOT
Time to rescue	min (EOT, Date of W26 visit)	EOT
Time to severe or documented hypoglycemia	See Section 3	Min (EOT+1, EOS)
Time to ESRD	min (EOS, Date of W26/re-allocated W26 eGFR value)	EOS
Time to eGFR decrease	min (EOS, Date of W26/re-allocated W26 eGFR value)	EOS
Time to UACR progression/improvement	min (EOS, Date of W26/re-allocated W26 UACR value)	EOS

Note:

Day 182 will be used if Date of Week 26 visit (or date of W26/re-allocated W26) is not available.

Date of EOS will be used if date of EOT is not available; Last contact date will be used if date of EOS is not available.

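### The protocol counts rescue from Day 1 to Week 26, but the SAP stops counting at the last IMP dose while keeping all randomized patients in the denominator

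*SAP*

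**What the plan says.** **Protocol.** Section 9.1.3 lists among the other efficacy endpoints: "Proportion of patients requiring rescue for hyperglycemia during 26-week double-blind Treatment Period". The heading of 6.1.2 gives the span of that period: "Double-blind Treatment Period (Day 1 to Week 26". Section 11.2 treats stopping IMP as an event inside the period, with a disposition category for "Patients who discontinued the IMP during the 26-week double-blind Treatment Period". Section 9.1.4.7 adds: "The use of rescue medications for hyperglycemia will be assessed and reported throughout the double-blind Treatment Period". Section 10.3.4 covers those who stop permanently: "Patients should be followed up according to the study procedures as specified in this protocol up to the scheduled date of study completion".

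**SAP.** Section 2.1.3.3 repeats the protocol's endpoint wording. Section 2.4.4.3 then says: "The number (%) of patients who used rescue therapy will be provided by treatment group during the 26-week core" and 52-week entire treatment periods, and points to 2.5.4. There the core treatment period runs from the first dose to the last dose taken no later than Visit 9 (Day 182 if that visit date is missing), followed by: "This is for defining EOT status at Week 26 and analyzing selected efficacy parameters (eg, rescued patients) during 26-week core treatment period".

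Table 5 censors time to rescue at "min (EOT, Date of W26 visit") for the first step and at EOT for the second. Appendix D gives ITT as the population for the rescue proportion, and 2.3.1.1 defines ITT as all randomized patients. Section 2.1.3 identifies a rescued patient by a tick on the e-CRF medication page, without requiring that the patient still be on IMP.

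**The concern.** One named endpoint has two windows. The protocol's is a calendar period that continues after IMP is stopped, whereas the SAP's ends with IMP. Because the denominator stays at all randomized patients, someone who stops IMP at Week 6 and starts rescue at Week 14 is in the denominator but not in the numerator.

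The narrower window also sits awkwardly within the SAP. Section 2.1.3 says efficacy data after IMP discontinuation are used. In Table 5 the time-to-event endpoints for ESRD, eGFR decrease and UACR are followed towards EOS, but time to rescue stops at EOT. A 26-week core study period already exists in 2.5.4, but it is reserved for end-of-study status. Randomized patients who were never dosed have no core treatment period, yet they belong to ITT. The legible entries in SAP Tables 1 and 2 do not list the narrower window as a change.

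What is at stake is interpretation. The primary HbA1c analysis keeps values obtained after IMP discontinuation and after rescue. A rescue rate meant to describe how much added therapy lies behind those values should cover the same time.

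**Working it through.** **No plan figure to reproduce.** Neither document states an expected rescue rate or IMP discontinuation rate. Every rate below is an assumption. Only the planned 260 per arm (SAP 1.1) comes from the documents.

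**Step 1: direction.** Let A be the ITT patients first rescued on IMP up to Week 26, and B those first rescued after the last dose but by Week 26. The SAP proportion is A/N and the protocol proportion is (A + B)/N. With the same N, the SAP figure is never higher, and it is lower whenever B is at least 1.

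**Step 2: size as a product.** Shortfall = (share stopping IMP unrescued before Week 26) × (share of those rescued between stopping and Week 26).
- Assume 10% and 20%: 0.10 × 0.20 = 2.0 points, or 260 × 0.02 = 5.2 patients. For example, 10.0% is reported instead of 12.0%.
- Over assumed ranges of 5–20% and 0–40%, the shortfall runs from 0 to 0.20 × 0.40 = 8 points (0 to 20.8 patients).

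**Step 3: constant hazards.** The time unit is 26 weeks. Assume 15% rescued in the absence of stopping and 12% stopping in the absence of rescue.
- Rescue hazard r = −ln(1 − 0.15) = 0.1625; stopping hazard d = −ln(1 − 0.12) = 0.1278.
- On-IMP (SAP) proportion = r/(r + d) × [1 − exp(−(r + d))] = 0.1625/0.2904 × 0.252 = 14.1%.
- Off-IMP addition = ∫₀¹ d·exp(−(r + d)t)·[1 − exp(−m·r·(1 − t))] dt, where m is the rescue hazard after stopping relative to on IMP.

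| m | Off-IMP addition (points) | Day 1 to Week 26 | Share of rescues missed |
|---|---|---|---|
| 1 | 0.9 | 15.0% | 6% |
| 2 | 1.7 | 15.8% | 11% |
| 3 | 2.4 | 16.5% | 15% |

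The SE of one arm's proportion is about √(0.15 × 0.85/260) = 2.2 points, so the shortfall is roughly 0.4 to 1.05 SE.

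**Step 4: between arms.** Assume placebo 15% rescued and 12% stopping, sotagliflozin 8% rescued and 18% stopping. The SAP risk ratio is 7.27/14.11 = 0.515.
- Hazard unchanged after stopping: 8.0/15.0 = 0.533.
- Hazard tripled in both arms: 9.35/16.52 = 0.57.
- A 30% risk per 26 weeks after stopping in both arms: 10.1/15.9 = 0.64. This needs a post-stop hazard of −ln(0.70) = 0.357, which is 0.357/0.1625 = 2.2 times the on-IMP hazard on placebo and 0.357/0.0834 = 4.3 times on sotagliflozin. Even here the risk difference moves only from 6.8 to 5.8 points, against an SE of about 2.9.

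The difference can move either way. With on-IMP rescue of 15% and 5%, and 20% of stoppers rescued later, the SAP difference is 10 points. The full-period difference is 8 points if 5% (placebo) and 15% (active) stop, 12 if 15% and 5% stop, and 10 if 10% stop in both.

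**Step 5: Kaplan-Meier.** Patients who stop IMP unrescued are censored at EOT, not counted as event-free to Week 26. With m = 1 the curve estimates the full-period 15.0%. It is biased only if stopping IMP is related to rescue risk.

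**The case against.** The best defence is that the SAP follows the protocol's idea of rescue. Protocol 8.2.1 has the investigator check dosing and compliance before rescue and keeps the rescued patient on blinded IMP; 8.8.2 says the same. Section 10.3.3 foresees adjustment of glycemic therapy when IMP is stopped, and 10.3.1 has other glucose-lowering drugs used during a temporary interruption recorded as concomitant medication. Therapy started after IMP could be read as replacing the stopped drug. The SAP choice would then be a while-on-treatment estimand. This is a reasonable intention, but neither document makes it a condition of the endpoint, and the e-CRF tick carries no such condition. If it was intended, it should be recorded as a departure from the protocol.

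It can also be said that post-IMP drug use is reported anyway. SAP 2.4.2 tabulates concomitant and posttreatment medications by arm, with antidiabetic drugs shown separately, and 2.4.4.3 promises a list of rescued patients. That helps, but none of it yields the protocol's Day 1 to Week 26 percentage.

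Three limits stand in full. The endpoint is descriptive and outside the testing hierarchy. The shortfall may be nil. SAP 1.6 reports that the first-step analysis was already run for top-line results, so any change now comes after it.

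**Conclusion.** The mismatch is explicit and should be corrected. As written, the SAP does not deliver the proportion the protocol defines, and its figure can err only downward. Under the assumptions in Step 3 the shortfall is about 0.9 to 2.4 points per arm; the true size cannot be derived from the documents.

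A reader might infer more than the documents support:
- **That the rate is certainly understated.** It is understated only if at least one patient is first rescued between the last dose and Week 26.
- **That the treatment comparison is seriously distorted.** The move in risk ratio from 0.52 to 0.64 needs a post-stop hazard 4.3 times the on-IMP hazard in the sotagliflozin arm. With an unchanged hazard it is 0.515 against 0.533.
- **That the Kaplan-Meier plot scores stoppers as non-events.** It censors them.
- **That the 52-week proportion has the same cut-off.** Only the EOT censoring of the 52-week curve is stated. The window for the 52-week proportion is not defined, which is itself a gap.
- **That the primary result is at risk.** Type I error, imputation and the HbA1c analysis do not depend on this window.

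**What to change.** 1. In SAP 2.4.4.3 and 2.5.4, report as the protocol endpoint the ITT proportion rescued from Day 1 (randomization if never dosed) to the Week 26 visit, or Day 182 if that date is missing, regardless of IMP status.
2. In Table 5, censor time to rescue at min(EOS, Week 26 visit date) for the first 26 weeks.
3. State the 52-week rescue window explicitly, and report the proportion and curve to EOS as well.
4. Keep the on-IMP count and curve as a supplementary analysis, labelled while-on-treatment.
5. Record that the change was made after the first-step analysis had produced top-line results.

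The cost is SAP wording plus a re-run of the rescue tables and Kaplan-Meier plots from medication data already collected. Patient management does not change. The downside is that the main rate will include glucose-lowering therapy started off IMP and recorded as rescue; the supplementary table separates it.

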2.5.5 Unscheduled visits

Unscheduled visit measurements of laboratory data, vital signs, and ECG will be used for computation of baseline, the last on-treatment value, PCSAs, and the shift summaries for safety or efficacy. They will be included in the by-visit summaries if they are re-allocated to scheduled visits (see [Section 2.5.4](#))

2.5.6 Pooling of centers for statistical analyses

Center will not be included in the statistical models for efficacy analyses. However, all centers within a country will be pooled, and country will be included as a fixed effect in a parametric statistical model (eg, ANCOVA etc) for primary and secondary efficacy endpoints. Countries with fewer than 5 randomized patients will be grouped, if patients from grouped countries are still fewer than 5, they will then be further grouped with the country with the lowest number of patients that is 5 or more.

